2.2. Study Design

[figure not shown]
This is a Phase 3, multicenter, randomized, double blind, vehicle controlled study to evaluate the efficacy and safety of crisaborole ointment 2% in Chinese and Japanese pediatric and adult subjects (ages 2 years and older) with mild to moderate atopic dermatitis involving at least 5% treatable BSA.

A total of approximately 384 subjects (approximately 50% for age ≥ 12 years old and approximately 50% for age < 12 years old) will be enrolled in the study from multiple sites in China and Japan. Following the screening period (up to 35 days prior to Baseline/Day 1), eligible subjects will be randomized at the Baseline/Day 1 visit in a 2:1 ratio to one of 2 treatment groups (crisaborole ointment, 2% BID; vehicle BID, respectively), the investigational product will be applied BID for 28 days to the Treatable BSA identified at Baseline/Day 1 and new AD lesions that appear after the Baseline/Day 1. The primary efficacy endpoint, percent change from baseline in EASI total score, will be assessed at Day 29.

Scheduled study visits for all subjects will occur at Screening, Baseline/Day 1, Day 8, Day 15, Day 22, Day 29 (End of treatment/Early termination). A follow up telephone call will be made by site staff to the subjects and/or parents/legal guardians on Day 36 and Day 60.

Japan participants who rolled over into study C3291027 without a Post Treatment Follow Up period prior to 21 Oct 2020 are considered completers in this study. A schematic of the study design is shown in [Figure 1](#).

Figure 1. Study Design Schematic

3. ENDPOINTS AND BASELINE VARIABLES: DEFINITIONS AND CONVENTIONS

3.1. Primary Endpoints

Efficacy endpoint: Percent Change from Baseline in EASI total score at Day 29.

Safety endpoint: TEAEs (including application site reactions) & SAEs and clinically significant changes in vital signs and clinical laboratory parameters.

3.2. Secondary Endpoints

Efficacy endpoints:

- Key secondary efficacy endpoints
 - Achievement of Improvement in ISGA (defined as ISGA score of clear (0) or almost clear (1)) at Day 29.

- Achievement of Success in ISGA (defined as an ISGA score of Clear (0) or Almost Clear (1) with at least a 2 grade improvement from Baseline) at Day 29.
- Change from Baseline in Peak Pruritus Numeric Rating Scale (NRS) at Week 4 - for subjects ≥ 12 years.
- Other secondary efficacy endpoints
 - Success in ISGA (defined as an ISGA score of Clear (0) or Almost Clear (1) with at least a 2 grade improvement from Baseline) over time.
 - Improvement in ISGA (defined as ISGA score of clear (0) or almost clear (1)) over time.
 - Percent change from Baseline in EASI total score over time.
 - Change from Baseline in %BSA over time.
 - Achievement of EASI-50 ($\geq 50\%$ improvement from baseline) over time.
 - Achievement of EASI-75 ($\geq 75\%$ improvement from baseline) over time.
 - Change from baseline in Peak Pruritus NRS over time - for subjects ≥ 12 years.
 - Changes from baseline in Patient Reported Itch Severity Scale over time - for subjects ≥ 6 years and < 12 years.
 - Change from baseline in Observer Reported Itch Severity Scale over time - for subjects < 6 years.
 - DLQI, CDLQI, IDQOL, DFI, POEM, PGIS/OGIS, PGIC/OGIC over time.

CCI [REDACTED]

- [REDACTED]
- [REDACTED]
- [REDACTED]
- [REDACTED]

[REDACTED]

[REDACTED]

[REDACTED]

[REDACTED]

[REDACTED]

[REDACTED]

[REDACTED]

[REDACTED]

[REDACTED]

3.4. Baseline Variables

For Peak Pruritus NRS, Patient/Observer Reported Itch Severity Scale and PGIS/OGIS, the average of the latest available 7-day scores immediately prior to Day 1 (including Day 1) will be used as the baseline. The baseline is considered missing if the daily scores are only available for less than four days. If the daily scores are available for more than three days, then the baseline is calculated as the average of the available scores.

Day 1 is defined as the first dosing date.

The baseline values of all other endpoints are defined as the last values collected prior to the first dose of study drug.

Baseline variables include

- Demographics;
- Height and weight;
- ISGA score;
- EASI total score;
- Peak Pruritus NRS, Patient/Observer Reported Itch Severity Scale;
- Treatable %BSA;
- DLQI/CDLQI/IDQOL;
- DFI;

- POEM;
- PGIS/OGIS;

█ [REDACTED]

These data will be summarized as part of the demographic characteristics and baseline characteristics.

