In-clinic dose application by study staff (1 st dose [preferred AM]) ⁿ		x						
At-home dosing, applied by subject or parent/legal guardian, as appropriate ^o		2 nd dose (PM) on Day 1, then BID through Day 28 ⁿ						
Dispense Dosing Diary		x	x	x	x			
Obtain and review Dosing Diary data and assess compliance			x	x	x	x		
Weigh investigational product tube(s) and dispense for at-home dosing		x	x	x	x			

Day [relative to start of study treatment (Day 1)]	Within 35 days prior to Day 1	Day 1	Day 8	Day 15	Day 22	Day 29 ^t	Day 36	Day 60
Window			±1 d	±3 d	±3 d	±3 d	±3 d	±3 d
Visit	Screening^d	Baseline				End of Treatment/ Early Termination	Follow up telephone Contact^f	Follow up telephone contact^r
Collect and weigh returned investigational product tube(s)			x	x	x	x		
Contraception Check	X	x	x	x	x	x	x	X

- a. Record all treatments (including medications and non-medication therapies) used for AD 90 days prior to screening and all other medications (including bland [non-medicated] emollients, over-the-counter drugs, vitamins, and antacids) used within 30 days prior to Screening.
 - b. Temperature, respiratory rate, pulse rate, and blood pressure taken in the seated or supine position, after the subject has been sitting or lying calmly for a minimum of 5 minutes. Position of recording must be consistent within subject through-out the study. At Baseline/Day 1 and Day 29, assessment of vital signs should precede blood draw for clinical laboratory tests.
 - c. Full physical examination including, but is not limited to the following organ or body systems: head, ears, eyes, nose, mouth, skin, heart and lung examinations, lymph nodes, musculoskeletal, abdomen (liver, spleen), and neurological systems. In addition, an assessment will be made of the condition of all AD involved skin.
 - d. Disease focused physical examination of all AD involved skin (in treatable and non-treatable areas) and evaluate any current or reported symptoms for clinically significant changes.
- █ [REDACTED]
- █ [REDACTED]
- g. Peak Pruritus NRS will be completed by subject (≥12 years), Patient Reported Itch Severity Scale will be completed by the subject (≥6 years and <12 years.), and Observer Reported Itch Severity Scale will be completed by observer [parent/legal guardian/other caregiver] when applicable) for patients <6 years in screening once daily prior to Day 1, and once daily from Day 1 to Day 29 before IP morning dose application preferably at the same time of each day if applicable.

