4.3. Randomization Criteria

Subject will be randomized into the study provided that the subject [or parent(s)/legal guardian] has signed an informed consent (or assent, if applicable) document to participate in the study, and the subject has undergone all screening procedures, and meets all inclusion and exclusion criteria for participation in the study at the baseline visit. A centralized computer generated randomization schedule will be used to assign subjects to the treatment groups. Subjects will be randomized in a 2:1 ratio to one of the 2 parallel treatment groups (Crisaborole ointment, 2% BID or Crisaborole placebo vehicle ointment BID).

Subjects will be assigned a subject identification number in the order of their screening for the study. The identifying number will be retained throughout the study.

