6.4. Study Period/Treatment Period

6.4.1. Baseline/Day 1 Visit

- a. The following procedures will be performed at the Baseline/Day 1 Visit BEFORE dosing with investigational product:
- Ask the subject or observer (parent/legal guardian/other caregiver) when applicable to complete the Peak Pruritus NRS/Patient Reported Itch Severity Scale/Observer Reported Itch Severity Scale and PGIS/OGIS QD (preferably same time of day each day if applicable) before IP morning dose applied starting at Baseline/Day 1 and continuing through Day 28 and at Day 29.
 - Ask the subject or observer when applicable to complete the POEM, DLQI, CDLQI, IDQOL, and DFI.
 - Assess and record any changes in the subject's prior and concomitant medications since the Screening Visit (if Screening and Baseline are 2 visits); see [Section 5.8](#) for medications prohibited prior to Baseline/Day 1 and during the study.
 - Obtain and record medical history.
 - Obtain vital signs (temperature, respiratory rate, pulse rate, and BP) in the seated or supine position, after the subject has been sitting or lying calmly for a minimum of 5 minutes; assessment of vital signs should precede blood draw for clinical laboratory tests.
 - Measure height and weight.
 - Perform a disease focused physical examination of all AD involved skin (in treatable and non-treatable areas) and evaluate any current or reported symptoms for clinically significant changes.
 - Complete the ISGA. ISGA must be completed prior to CCI [REDACTED] the EASI assessment (Note: The ISGA score must be 2 or 3 at Baseline/Day 1 for subject to be eligible for the study).
[REDACTED]
 - Complete the EASI assessment, after completing the ISGA CCI [REDACTED]
[REDACTED]

- Calculate subject's Treatable %BSA.
- Confirm subject's eligibility based on the [Inclusion Criteria](#) and [Exclusion Criteria](#), including confirming acceptable methods of birth control for female subjects of childbearing potential.
- Assess and record any AEs/SAEs.
- Draw blood for clinical laboratory tests on Day 1 prior to initial dosing; assessment of vital signs should precede blood draw for clinical laboratory tests; testing includes serum chemistry and hematology.

Note: If the screening serum chemistry and hematology tests are performed within 15 days prior to Day 1, whether the Day 1 serum chemistry and hematology tests are to be performed will be at the discretion of Principle Investigator (PI) or designee.

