5.3. Methods to Manage Missing Data

Multiple Imputation based on Markov Chain Monte Carlo (MI-MCMC)

Missing ISGA scores will be derived for the analysis using the method of MCMC multiple imputation. Multiple imputation and subsequent analysis will involve the following four principal tasks:

1. Calculate the number of missing values to be imputed by MCMC (nmiss) for the Day 29 value.
2. Create a data set, one for each treatment group, of subjects with observed values and those needing imputation by MCMC. The missing ISGA values in each data set will be filled in using the MCMC method “10× nmiss” times to generate “10 × nmiss” data sets. The resulting data sets for each treatment group will be combined into one complete data set by imputation. The imputed values will be rounded to the nearest value of 0, 1, 2, 3, or 4.
3. For each complete data set, derive dichotomous variables Success in ISGA (Clear [0] or Almost Clear [1] with a 2-point change from Baseline) and Improvement in ISGA (Clear [0] or Almost Clear [1]). The estimated treatment effect and its standard error for each complete data set will be calculated with the method specified in [Section 5.2.1](#).
4. Combine the estimated treatment effects and standard errors from the above into a single inference using Rubin’s formulae as implemented in SAS PROC MIANALYZE.

Success in ISGA and Improvement in ISGA will be derived from the imputed complete ISGA data sets.

For EASI-50 and EASI-75, missing EASI total scores will be imputed in the same way as missing ISGA scores except no rounding will be done to the imputed values. Missing EASI-50 and EASI-75 values will be derived from the imputed complete EASI data sets.

Non-Responder Imputation (NRI) Non-Responder Imputation (NRI) as another alternative way of handling missing data will also be used in Supportive analyses. If a subject has missing data for a binary endpoint at a scheduled visit, this subject will be defined as a non-responder for that endpoint at that visit.

Repeated measure modeling with no explicit imputation For continuous endpoints, missing values are assumed missing at random (MAR) and will be handled by MMRM.

In general, for descriptive statistics and time to event analysis, missing values will not be imputed.

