6.2.3.1. Main Analysis

- Estimand strategy: Hypothetical.
- Analysis set: FAS.
- Analysis methodology: change from baseline to Week 4 (Days 23-29) in weekly average of Peak Pruritus NRS for subjects ≥ 12 years, will be analyzed using a MMRM that includes treatment group, visit, and treatment group-by-visit interaction as factors and

baseline value as a covariate. Within-subject variability will be accounted for using a random effect with the first-order autoregressive (AR(1)) covariance matrix.

- Intercurrent events and missing data: Data after treatment discontinuation prior to Day 29 will not be considered. The weekly average is considered missing if Peak Pruritus NRS scores are missing for more than three days. If the scores are missing for less than four days, then the weekly average is computed as the mean of the scores for the non-missing days. Missing weekly average values will not be explicitly imputed and will be assumed to be MAR.
- Reporting results:
 - Tables: The sample size, LS mean of change from baseline and 95% CI for each treatment, LS mean of difference and the corresponding 95% CI, and p-value will be presented at Week 4.

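### Does the missing-baseline rule for the itch diary, which has no fallback, damage the Week 4 Peak Pruritus NRS analysis?

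*SAP*

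**What the plan says.** SAP 3.4 (Baseline Variables) states for the itch scales and PGIS/OGIS that "the average of the latest available 7-day scores immediately prior to Day 1 (including Day 1) will be used as the baseline", and then: "The baseline is considered missing if the daily scores are only available for less than four days". With four or more scores, the baseline is the mean of those present. Table 5 in SAP Appendix 2.1 sets the baseline window at Days -6 to 1. For every other endpoint, the baseline is the last pre-dose value.

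SAP 6.2.3.1 analyses change from baseline to Week 4 in subjects aged 12 or over in the FAS, by MMRM with baseline as a covariate. For the weekly means it says: "The weekly average is considered missing if Peak Pruritus NRS scores are missing for more than three days". It continues: "Missing weekly average values will not be explicitly imputed and will be assumed to be MAR". SAP 5.3 says of continuous endpoints in general that "missing values are assumed missing at random (MAR) and will be handled by MMRM".

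On collection, note g to the protocol's Schedule of Activities asks for a score once daily in screening and then "once daily from Day 1 to Day 29 before IP morning dose application". Protocol 6.4.1 repeats that the score is taken "before IP morning dose applied starting at Baseline/Day 1". Protocol 4.3 allows randomization only if "the subject has undergone all screening procedures".

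**The concern.** A subject with three or fewer scores in the baseline window has no baseline, hence no change score at any week and no covariate value. The MMRM cannot use that subject. The missing-at-random text does not help, because it deals with missing outcomes in subjects who can enter the model.

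The analysis is nevertheless labelled FAS, and the estimand population in SAP 2.1 carries no condition on diary completeness. Usable information also seems to be discarded, since a pre-dose Day 1 score would often exist and most other endpoints accept a single pre-dose value. At stake would be power on the last key secondary endpoint in the testing sequence. The same rule governs the itch scales for ages 6 to 11 and under 6, and PGIS/OGIS.

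**Working it through.** **1. Is the rule complete and consistent?**

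| | Window | Days | Value exists if | Otherwise |
|---|---|---|---|---|
| Baseline (SAP 3.4, Table 5) | Days -6 to 1, no Day 0 | 7 | at least 4 scores | missing |
| Week 4 (SAP 6.2.3.1, Table 5) | Days 23 to 29 | 7 | at most 3 missing, so 7 − 3 = at least 4 scores | missing |

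The two rules are identical. The change score is a difference between two means, each resting on at least four of seven days. Two analysts following the SAP would exclude the same subjects. The phrase about the latest available scores could be read as reaching further back into screening, but Table 5 closes that reading.

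**2. Can it bias the comparison?** Exclusion depends on diary entries up to Day 1. Protocol 7.1.6 has questionnaires completed on visit days before any other procedure, and Protocol 6.4.1 places the score before dosing and lists randomization later. Exclusion therefore cannot depend on the assigned arm. Randomization still protects the comparison among those who remain, and type I error is unaffected.

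**3. What could it cost in precision?** The plan states no power for the NRS endpoint. Its only power figure (Protocol 9.1: 384 subjects, 256:128, about 90%) is for EASI, and it does not carry over.

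Inputs: about 50% of 384 subjects aged 12 or over (SAP 2.2) gives 192, or 128:64 at 2:1; two-sided 0.05 (SAP 5.1). The share lost, f, and the full-data power, P, are assumptions.

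- SE factor = 1/√(1 − f)
- Power = Φ((1.960 + z_P)·√(1 − f) − 1.960), with z_P = 0.8416 for 80% and 1.2816 for 90%

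Example, f = 5%, P = 80%: 1/√0.95 = 1.026; 2.8016 × 0.9747 − 1.960 = 0.771; Φ(0.771) = 0.780.

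| f (assumed) | Subjects lost | SE factor | Power from 80% | Power from 90% |
|---|---|---|---|---|
| 2% | 3.8 | 1.010 | 79.2% | 89.4% |
| 5% | 9.6 | 1.026 | 78.0% | 88.5% |
| 10% | 19.2 | 1.054 | 75.7% | 86.8% |
| 20% | 38.4 | 1.118 | 70.7% | 82.6% |

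**4. What would a fallback to the available scores recover?** Not necessarily all of this, because subjects with sparse screening diaries may also have sparse treatment diaries. If half of them lack usable post-baseline means (assumed), the effective loss falls from 2%, 5% or 10% to 1%, 2.5% or 5%. Power from 80% then returns to 79.6%, 79.0% or 78.0%, a gain of about 0.4, 1.0 or 2 points.

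**5. What would a fallback cost?** If daily errors are independent with variance σ² (assumed), a lone score has error variance σ², against σ²/4 for the poorest baseline now allowed and σ²/7 for a full week. Week 4 would still need four days, so the two ends of the change score would no longer match. The Day 1 score may also be untypical: Protocol 5.8.1 bars emollients on treatable lesions for the preceding 24 hours, and Protocol 7.1.6.1 has the NRS ask about that same period. A change in SAP 3.4 would also reach the scale for ages 6 to 11, which has five points and asks about the current day.

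**6. Is a large share plausible?** Daily scores are required throughout screening (Protocol 6.3), and all screening procedures must be done before randomization (4.3). Screening results must be reviewed first (6.3), and the blood tests go to a central laboratory (7.2.1). Washouts of 7 or 14 days apply to several topical treatments (5.8.1). These points suggest few affected subjects, but they do not prove it.

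**7. Would the loss be visible?** Baseline NRS is among the summarized baseline variables (SAP 3.4), SAP 5.2.2 includes sample size in continuous summaries, and the Week 4 table gives sample size by arm (6.2.3.1).

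**The case for a change.** The strongest case accepts the four-of-seven convention and asks only that the consequence be softened. No minimum screening length is set, and Protocol 6.4.1 allows that Screening and Baseline may not be two visits. A subject who starts the diary fewer than three days before Day 1 cannot reach four scores however diligent. If that were common, a 20% loss would raise the standard error by 11.8%. The PPAS criteria in SAP 4 exclude subjects with a missing Week 4 NRS but are silent on a missing NRS baseline, so a subject could count in both analysis sets and appear in neither model. A fallback needs little text and no new data.

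A simulation supports some gain. It used assumed variances, with 5% or 10% of subjects having only a Day 1 score. Using that score added 1.2 to 3.4 power points if all of them had Week 4 data, and 0.5 to 2.4 if half did not. However, it used a Week 4 ANCOVA in place of the MMRM. The affected subjects differed from the rest only in the assumed Day 1 shift and missing Week 4 data, so its near-zero bias was largely built in.

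What stands is that the exclusion follows from the model and is not spelled out, that the affected share is unknown, and that the analysed group is the FAS with a valid baseline. None of this makes the rule wrong. For the other endpoints, the last pre-dose value is their primary definition, not a fallback that the NRS lacks. Accepting fewer days in exchange for more subjects is a trade on which reasonable statisticians differ.

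**Conclusion.** The concern does not hold. The loss of a subject without a baseline is real, but it follows from a complete rule, fixed in advance and identical before and after treatment starts. It leaves the arm comparison unbiased and type I error intact. It does not touch EASI or ISGA. For the key secondary family, its reach is one endpoint, last in the sequence, in about half the subjects.

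The cost is precision alone: a standard error 1.0% to 5.4% larger and 0.8 to 4.3 points off an assumed 80% power, if 2% to 10% of those subjects lack a baseline. Those shares and that power are assumptions. The screening requirements make a large share unlikely without excluding it. A looser threshold would return part of that loss in exchange for noisier and possibly untypical baselines. The window is already fixed by Table 5, and the planned summaries already show sample sizes. No change is needed.

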3.5. Safety Endpoints

Safety will be assessed by the spontaneous reporting of AEs, SAEs, physical examinations, vital signs, and clinical laboratory results in all subjects who receive at least one dose of the investigational product. Unscheduled safety assessments may be performed at any time during the study to assess any perceived safety concerns.

Safety data will be descriptively summarized and will be presented in tabular. No imputation will be made for missing safety data. The following safety data will be summarized:

- TEAEs, including SAEs;
- Clinically significant changes in vital signs;
- Clinically significant changes in laboratory parameters.

3.5.1. Adverse Events

An adverse event will be considered as a TEAE if the event started after the first dose of treatment regardless of whether a similar event of equal or greater severity existed in the baseline period.

Adverse events will be assessed by the spontaneous reporting of:

- Incidence of TEAEs;
- Incidence of SAEs;
- Incidence of AEs leading to discontinuation.

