6.2. Time Windows for Study Procedures

Allowable time windows for visits/contacts are as follows:

- Screening visit: up to 35 Days prior to Day 1/baseline;
- Day 1 Visit: Day 1;
- Day 8 Visit: Day 8 \pm 1 day;
- Day 15 Visit: Day 15 \pm 3 day;
- Day 22 Visit: Day 22 \pm 3 day;
- Day 29 End of Treatment Visit: Day 29 \pm 3 day;
- Follow up telephone contact 1: Day 36 \pm 3 day;
- Follow up telephone contact 2: Day 60 \pm 3 day.

Refer to the [Schedule of Activities](#) for a complete list of assessments to be performed during the study.

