- Collect complete medical history, including onset of AD (date of diagnosis, as specifically as known).
- Measure height and weight.
- Perform a complete physical examination and confirm clinical diagnosis of AD per Hanifin and Rajka criteria ([Appendix 2](#)).
- Record all prior and concomitant medications (including all medications and non-medication therapies) used for AD used within 90 days prior to screening and all other treatments, including bland emollients, over-the-counter- drugs, vitamins, and antacids, used within 30 days prior to Screening.

- If a subject is using a prohibited medication (or non-medication therapy) at the time of Screening, the investigator or his/her designee will provide instructions on discontinuing the prohibited medication or therapy (ie, a washout period) at Screening.
- If a subject will be undergoing washout of a prohibited medication as directed by the investigator or his/her designee, the subject's tentative eligibility will be confirmed pending successful completion of the washout (to be confirmed at Baseline/Day 1 Visit).
- Assess for AEs/SAEs, starting from the time of informed consent and assent, as applicable.
- Urine pregnancy test (female subjects of childbearing potential only).
- Serum chemistry and hematology.
- FSH (to confirm postmenopausal status in females who are amenorrheic for at least 12 consecutive months).
- Complete the ISGA (will be completed at screening for all subjects including screen failure subjects, if a subject is screen failed before above procedures are completed, then related data will not be collected).
- Calculate subject's Treatable %BSA.
- Review subject's tentative eligibility according to the Inclusion and Exclusion Criteria.

Note: The results of all screening evaluations must be reviewed for clinical significance by the investigator or his/her designee prior to randomization of the subject on Baseline/Day 1.

- Contraception check: Confirm and document in source documents that proper contraception has been reviewed for the female subject of child bearing potential and their partner as appropriate, and the subject's agreement to use appropriate contraception methods throughout the study.
- Schedule the Baseline/Day 1 Visit and all future study visits for the subject's study visit calendar, and review the calendar with the subject and/or parent/legal guardian.

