8.1.4. Time Period for Collecting AE/SAE Information

The time period for actively eliciting and collecting AEs and SAEs (“active collection period”) for each subject begins from the time the subject provides informed consent, which is obtained before the subject’s participation in the study (ie, before undergoing any study-related procedure and/or receiving investigational product), through and including a minimum of 28 calendar days after the last administration of the investigational product.

For subjects who are screen failures, the active collection period ends when screen failure status is determined.

All nonserious AEs and SAEs occurring in a participant during the active collection period, which begins after obtaining informed consent/assent as described in Section 8.1.4, will be recorded on the AE section of the CRF.

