8.2. Definitions

8.2.1. Adverse Events

An AE is any untoward medical occurrence in a study subject administered a product or medical device; the event need not necessarily have a causal relationship with the treatment or usage. Examples of AEs include, but are not limited to:

- Abnormal test findings;
- Clinically significant signs and symptoms;
- Changes in physical examination findings;
- Hypersensitivity;
- Progression/worsening of underlying disease;
- Drug abuse;
- Drug dependency.

Additionally, AEs may include signs and symptoms resulting from:

- Drug overdose;
- Drug withdrawal;
- Drug misuse;
- Drug interactions;
- Extravasation;
- Exposure during pregnancy (EDP);
- Exposure via breastfeeding;

- Medication error;
- Occupational exposure.

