8.3. Severity Assessment

If required on the AE page of the CRF, the investigator will use the adjectives MILD, MODERATE, or SEVERE to describe the maximum intensity of the AE. For purposes of consistency, these intensity grades are defined as follows:	
MILD	Does not interfere with subject's usual function.
MODERATE	Interferes to some extent with subject's usual function.
SEVERE	Interferes significantly with subject's usual function.

Note the distinction between the severity and the seriousness of an AE. A severe event is not necessarily an SAE. For example, a headache may be severe (interferes significantly with the subject's usual function) but would not be classified as serious unless it met one of the criteria for SAEs, listed above.

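### The TEAE definition rests on onset alone, so an adverse event that starts in screening and worsens on treatment under the same record is not treatment-emergent

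*SAP*

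**What the plan says.** SAP 3.5.1 states: "An adverse event will be considered as a TEAE if the event started after the first dose of treatment". The same sentence continues "regardless of whether a similar event of equal or greater severity existed in the baseline period". The protocol uses the term TEAE in Sections 2 and 9.3 but does not define it.

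Protocol 8.1.4 says that the active collection period "begins from the time the subject provides informed consent". Protocol 6.2 sets the pre-dose window: "Screening visit: up to 35 Days prior to Day 1/baseline". Protocol 6.3 has sites assess adverse events throughout that window.

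Protocol 8.3 has the investigator use mild, moderate or severe "to describe the maximum intensity of the AE", on condition that the CRF page asks for it. Protocol 8.2.1 includes "Progression/worsening of underlying disease" among its examples of adverse events.

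TEAEs stand in the primary safety endpoint (Protocol 2, SAP 3.1). SAP 3.5.1 also lists the incidence of SAEs and of adverse events leading to discontinuation as items of their own. SAP 4 puts back into the per-protocol set (PPAS) those subjects who stop early for lack of efficacy or for a TEAE judged related to treatment.

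**The concern.** A treatment-emergent rule should pick up what changes after dosing begins. A rule based on onset alone picks up what starts after dosing but not what gets worse.

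The gap can arise in this trial. Protocol 5.8.1 and 6.3 have prohibited treatments, including topical corticosteroids and calcineurin inhibitors, stopped at Screening for washout. An adverse event with onset before Day 1 that is still open at first dose is therefore foreseeable. If it goes from mild to severe on treatment, its start date still precedes the first dose, and the TEAE tables omit it.

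Two things are at stake. The first is completeness of the primary safety endpoint: the omission applies to both arms but removes more events from whichever arm has more worsening. The second is membership of the PPAS, which is the supplementary set for the primary and key secondary efficacy endpoints (SAP 6.1.1.2, 6.2.1.2, 6.2.2.2 and 6.2.3.2).

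**Working it through.** No arithmetic applies, because the point concerns a classification rule. The check is to apply SAP 3.5.1 to each type of event and then look in both documents for anything that changes the result.

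1. Starts after first dose, nothing similar before: TEAE.
2. Starts after first dose, with a similar event at baseline of equal or greater severity: TEAE, by the second half of the sentence.
3. Starts in screening, ongoing at first dose, unchanged: not a TEAE, as one would expect.
4. Starts in screening, ongoing at first dose, worsens on treatment, same record: not a TEAE, because the start date is before the first dose.
5. As case 4, but the site closes the record and opens a new one dated after first dose: TEAE, because it becomes case 2.

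The result for a worsening event therefore depends on whether the site keeps one record (case 4) or opens a second (case 5). Neither document tells sites to open a new record when severity rises, and neither asks for the date of an intensity change. Protocol 8.3, where it applies, asks for one maximum intensity per event, which points towards case 4. A single maximum also cannot show whether the peak came before or after the first dose, so the analyst could not recover the worsening later from that field.

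What case 4 loses:

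- An event that becomes serious can still appear under the incidence of SAEs in SAP 3.5.1.
- An event that leads to discontinuation can still appear under the incidence of adverse events leading to discontinuation.
- A non-serious event that worsens without discontinuation appears in neither list. This is the main loss.

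Effect on the PPAS: suppose a subject discontinues because a case 4 event worsened and the investigator relates the worsening to treatment. Under 3.5.1 that event is not a TEAE, so the subject is not returned to the PPAS on that ground under SAP 4. A subject who discontinues for the same reason with an event that started after first dose is returned.

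**The case against.** The strongest reply is that the rule is deliberately inclusive where it matters. Its second half counts every newly started event, however bad the baseline was. A reaction to the product cannot begin before its first application, so application site reactions are all captured. Atopic dermatitis itself is taken as medical history (Protocol 6.3) and worsening of underlying disease is an adverse event in its own right (Protocol 8.2.1), so a flare that starts after first dose has its own post-dose start date and counts. All of this stands. A reader might infer that the rule hides on-treatment skin aggravation in general, or application site pain in particular; the documents do not support that.

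A reader might also infer that such events can never be treatment-emergent. That goes too far, because it assumes one record per event. The documents point that way but do not require it, and the severity field in Protocol 8.3 is itself conditional.

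The separate lists for SAEs and discontinuations are a fair answer for those events, with one reservation: Protocol 9.3 and SAP 3.5 describe the summary as covering TEAEs with SAEs included among them, so it is not fully clear that an SAE with pre-dose onset would be shown.

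The sponsor's safety rulebook, cited in SAP 6.1.2 and 6.6, may treat worsening differently. Its content is not in the documents, and SAP 3.5.1 states its own definition, so it cannot be relied on to close the gap.

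Eligibility also narrows the pool: unstable disease and significant active infection are excluded, and ISGA must be 2 or 3 at Day 1 (Protocol 4.1 and 4.2). This limits the number of affected events but does not reduce it to zero.

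**Conclusion.** The gap is real and follows from the stated definition. An adverse event collected in screening, ongoing at Day 1 and worsening on treatment under the same record falls outside the TEAE component of the primary safety endpoint. The practical loss is mainly non-serious events that worsen without discontinuation, with a secondary effect on who is returned to the PPAS.

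The size cannot be computed, because the documents give no rate of adverse events ongoing at first dose and none for worsening. It is tempting to attach a count. If one assumed that 3% to 5% of subjects had an adverse event ongoing at Day 1, that would be 384 × 0.03 = 11.5 to 384 × 0.05 = 19.2, or about 12 to 19 subjects. Nothing in the documents anchors that range, and it counts subjects with an ongoing event, not subjects who worsen. On that assumption it is a ceiling, not an estimate. The true effect is probably small.

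The conclusion assumes that sites keep one record for a continuing event and that the unseen rulebook does not override SAP 3.5.1. The change is still worth making, because the rule bears on a primary endpoint and is cheap to repair.

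**What to change.** In SAP 3.5.1, extend the definition to an event that started before the first dose and increased in severity or became serious after the first dose.

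State how the worsening is captured, because the clause cannot be applied from maximum intensity alone. Either have sites enter the worsening as a new adverse event record with its own start date, or have them record a dated change in intensity. Choose one method, so that the same worsening is not entered twice.

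The current SAP is dated 18 September 2021, and Protocol 3 refers to subjects who had already rolled over to the extension study before 21 October 2020. Dated severity will therefore be missing for some subjects. For subjects who completed without it, list separately the adverse events with pre-dose onset that were ongoing at first dose, with maximum intensity, seriousness and action taken.

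If onset alone is what the sponsor intends, say so in 3.5.1 and provide that listing for all subjects.

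The cost is one clause in the SAP, a CRF completion instruction with the extra data entry it brings, one listing, and TEAE counts that may rise slightly.
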